Candidates who have already been on conservative therapy for 3 months or more without a documented decrease in proteinuria of >50% as compared to a value from within the last 3 to 12 months do not need to fulfill the run-in requirement as long as their local labs indicate that proteinuria remains $\geq 5\text{g}/24\text{h}$. These individuals should proceed directly to full screening as part of the Time 0 visit and do not require a formal screening visit. Review of the eligibility criteria, lab requirements, and the review and signing of the informed consent form will take place at the Time 0 visit for these individuals. However, retrospective data from at least two previous time points (approximately 3 months prior to obtaining consent plus one more time point within the previous year) will still be collected whenever possible. Retrospective data collection needs to include proteinuria, urine creatinine, creatinine clearance, Uprot/Ucrea ratio, systolic blood pressure, diastolic blood pressure, serum creatinine, and serum albumin values.

Patient monitoring and evaluation

Patients will be followed for 2 years following randomization to monitor for the occurrence of adverse events, late remissions, relapses, GFR changes and development of

end stage renal disease. The first 12 months of the study will be considered as the treatment period while the remaining 12 months will be considered as an observational period including the period of tapering to discontinuation in the Cyclosporine arm. In addition, as described later in the protocol (see ancillary studies) we will seek permission to follow the remission cohort (i.e., those in PR or CR at 12 months or CR at 6 months as well as those who are not in remission but have a $\geq 50\%$ reduction in proteinuria from baseline by month 12) for an additional 12 months of observation beyond the previous end point of observation of 24 months to monitor for relapses and changes in PLA2R.

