For those patients in the Cyclosporine arm, **Cyclosporine trough level measurements will be done every 2 weeks +/- 3 days after initiation of Cyclosporine until levels are stable and at target. Potassium and creatinine will also be checked in conjunction with CSA level. If Cyclosporine dose is changed during treatment, potassium, creatinine and CSA level will be rechecked every 2 weeks +/- 3 days until levels are stable and at target.** Cyclosporine levels will also be assessed whenever serum creatinine rises by $>30\%$ without a recognizable reason such as volume depletion, additional drugs, sepsis, etc. Patients who cannot tolerate the medications and/or who are treatment failures at 6 months will exit the study at 6 months (i.e., the 6 month visit and accompanying data collection should still occur). Patients who go in to complete remission will discontinue study drug but will continue with full visit follow-ups until month 24 as scheduled. However, the therapeutic/management plan for these patients will be solely at the discretion of the managing nephrologist although while in CR no further immunosuppressive therapy is recommended. Likewise, patients who relapse from either a partial or complete remission or who are not in partial or complete remission by the end of the treatment period (i.e., 12 months) will continue with the visit schedule, but the therapeutic/management plan will be solely at the discretion of the managing nephrologist. Finally, for patients who temporarily stop taking Cyclosporine, there are three possible scenarios:

1. Patients who discontinue Cyclosporine for < 2 weeks may simply be restarted on the study drug and continue to fully participate in the trial. The treatment is to be restarted at its former dose and the patient returned to the regularly scheduled follow-ups including the periodic sampling for assessing potassium, creatinine and CSA trough levels.
2. Patients who discontinue Cyclosporine for ≥ 2 weeks, but < 4 weeks may also be restarted on the study drug at its former dose and fully participate in the trial, but the temporary discontinuance will be logged as a protocol deviation and the missed treatment days will be made up at the end of month 12. This is to ensure that all patients receive approximately 12 months of treatment with study drug.

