Sample size estimation: The primary study goal is to compare the long-term efficacy of RTX (given at baseline and repeated at 6 months) with CSA (12 months treatment + 2 months taper) using proteinuria response 24 months after randomization. Proteinuria positive response will be defined as attaining and maintaining CR or PR at 24 months after randomization. We propose to establish that the RTX treatment is non-inferior to the CSA. RTX will be considered non-inferior to CSA if the response rate of the RTX arm is at most 15% worse than that of CSA arm. In addition we will compare the quality of life (QOL) and adverse event (AE) profile over the course of the treatment period. The preliminary data has indicated that CSA is effective in inducing a CR/PR of proteinuria in between 60 and 75% of MN cases.^{48, 51} However, nephrotic syndrome (NS) relapses may be as high as 50% once CSA is discontinued.⁸⁵ Thus, we estimate a CR/PR rate in patients treated with CSA of 30-50% at 24 months after randomization.⁸⁵ Similar remission and relapse rates with the use of Tacrolimus (another calcineurin inhibitor) have been reported by Praga et al.⁵⁶ In this latter study, almost half of the MN patients had a relapse of the nephrotic syndrome after tacrolimus was discontinued.⁵⁶ On the other hand, based on the long term follow up on the 35 patients treated with RTX from our 2 studies, we estimate the relapse rate to be <10% at 24 months.^{71, 75} We observed a CR/PR rate at 12 months, very similar to the rate for calcineurin inhibitors i.e. 60%, and in our second study completed recently, we observed an 80% CR/PR rate at 24 months, implying that RTX had a ~20% failure rate with 95% (CI 6% to 44%). To be conservative for the sample size estimation, we considered a maintained CR/PR rate at the low end of our previous experience, 55% CR/PR for RTX at 24 months and at the high end of our experience with CSA (CNI therapy) CR/PR for CSA of 45%. We propose a non-inferiority trial with non-inferiority margin $\delta = 15\%$, with the null hypothesis of $\pi_{RTX} - \pi_{cyclosporine} < \delta$, where π_{RTX} and $\pi_{cyclosporine}$ are the proportions of patients with CR/PR at 24 months in treatment arms of RTX and CSA, respectively. Under these assumptions, and a one sided alpha of 0.025, enrollment of 63 evaluable patients per study arm is required to achieve 80% power to show that the RTX is not inferior. For the intent to treat (ITT) analysis we will consider all patients lost to follow up to be non-responders so no correction to the sample size is needed for dropouts. With 63 patients per arm we will have 80% power to detect moderate differences of .6 standard deviations for continuous measures or around .25 for proportions for the comparisons of the QOL and AEs.

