
Statistical and Analytical Plan: All demographics and entry laboratory data will be summarized by treatment group. Frequency distributions will be used to describe categorical values and basic summary statistics (mean, standard deviation, median, and inter-quartile range) will be used to describe continuous values. To provide more reliable estimates and minimize the “regression to the mean effect” duplicate urine measurements obtained at baseline (Time 0), 6, 12, 18 and 24 months will be averaged. The chi-square test and logistic regression will also be used to compare the percent of patients with remission at 6, 12, 18, and 24 months adjusting for treatment center and the baseline

proteinuria (UP<8g/24h vs >=8g/24h). Odds ratios and associated 95% confidence intervals will be estimated. The formal test for the primary endpoint will be based on the significance of the treatment group factor in the logistic regression model for UP failure at month 24. The Wilcoxon rank-sum test and ordinal logistic regression will be used to compare the ordered remission status outcome (1=CR, 2=PR, 3=NR) between treatment groups. Longitudinal methods for categorical outcomes (e.g. generalized estimating equation or GEE models) will be used to compare remission status profiles between treatment arms. Unless otherwise noted, all tests will be two-sided with alpha level 0.05.

For repeated measures such as urine protein, individual rates of change will be estimated using within-patient linear regression analyses (including data from all visits). Because of the non-linearity of the changes in proteinuria log transformation estimates will be used. Renal function readings will be censored at initiation of dialysis or renal transplant. Additionally, mixed effects models, assuming a random center effect, and a random slope of creatinine clearance and/or reciprocal of creatinine and intercept for each patient will be fit using data from all visits. These models allow comparison of the average slope between groups, while taking into account that each patient's slope may be based on a variable number of readings. Treatment group comparisons regarding quality-of-life scales will be done using repeated measures analyses and mixed effects models.

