Adverse events (both patient and event counts) will be tabulated by body system, severity and, for each severity, by investigator-assessed relationship to study drug. Group comparisons for adverse events with 4 or more occurrences will be done using chi-square or Fisher's exact test. The last RTX injection is at 6 months and the tapering of Cyclosporine will be completed by the end of month 14. Hence, the adverse events analyses will focus on events through month 18, allowing these additional months for potential lingering Cyclosporine or RTX complications.

The analysis of the primary endpoint (urine protein failure at month 24) will be intent-to-treat (ITT), and will include all randomized subjects in the analysis. For those without a 24 month visit, the 18 month visit results will be used if available, otherwise they will be assumed to have failed at 24 months. Per protocol (PP) analyses will also be done including only those subjects who receive a full course of study medication and who have a 24 month visit.

Interim analyses: No interim analyses for efficacy will be performed during the trial, however safety data will be compiled and reviewed approximately every six months or at the request of the Data and Safety Monitoring Board.

Investigator and Coordinator Training: In order to make efficient use of funding, annual investigator and coordinator meetings will be coordinated with national nephrology meetings where possible. It is expected that the majority of the training will occur through web-based technology and will be coordinated through the data management and coordinating Center.

The **Data Management and Coordinating Center (DMCC)** is located at the Applied Health Research Center (AHRC) at St. Michael's Hospital/University of Toronto. The DMCC will be responsible for facilitating all aspects of the study planning, training, implementation, data collection and analysis.

The clinical information collected for this study will be stored at the DMCC at the Applied Health Research Centre of St. Michael's Hospital in Toronto, ON, Canada and also sent to a federal data repository held by the Office of Rare Diseases Research (ORDR) and located at the University of South Florida (USF) in Tampa, FL.

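### Minor: with 63 per arm at two-sided 0.05, 80% power corresponds to about 0.5 SD, not the stated 0.6 SD, where power is about 92%

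*Combined protocol and SAP*

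**What the plan says.** Under Statistical Methods and Analysis, the sample size paragraph first derives 63 per arm for the primary non-inferiority comparison. It then says of the QOL and adverse event comparisons: "With 63 patients per arm we will have 80% power to detect moderate differences of .6 standard deviations for continuous measures". The same sentence gives a difference of around 0.25 as its counterpart for proportions.

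The Statistical and Analytical Plan sets the significance level: "Unless otherwise noted, all tests will be two-sided with alpha level 0.05". Nothing different is noted for QOL or adverse events. For QOL the plan says: "Treatment group comparisons regarding quality-of-life scales will be done using repeated measures analyses and mixed effects models".

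Three other statements bear on how many patients contribute QOL data:
- The sample size paragraph sets the scope: "we will compare the quality of life (QOL) and adverse event (AE) profile over the course of the treatment period".
- Patient monitoring and evaluation defines that period: "The first 12 months of the study will be considered as the treatment period".
- For patients who leave as treatment failures or for intolerance, that section adds that "the 6 month visit and accompanying data collection should still occur".

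On missing primary outcomes there are two statements. The sample size paragraph says "we will consider all patients lost to follow up to be non-responders" in the intention-to-treat analysis. The analysis plan says that, without a 24-month visit, "the 18 month visit results will be used if available, otherwise they will be assumed to have failed at 24 months".

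**The concern.** A power statement should follow from its own sample size, significance level and power, and this one does not. At 63 per arm and two-sided 0.05, a difference of 0.6 SD is well above what 80% power requires. The 0.25 in the same sentence is close to the actual detectable difference for proportions, so a reader will take 0.6 SD in the same way.

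Better quality of life is part of the fourth specific aim, and QOL is a listed secondary endpoint. The power statement tells a reader how to interpret a QOL comparison that shows no difference. As written, it understates the sensitivity of that comparison by about 0.1 SD if all 63 per arm contribute.

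The two missing-outcome statements raise a separate wording problem. A patient in remission at month 18 with no later visit is a non-responder under one and a responder under the other.

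**Working it through.** **Inputs from the documents.** n = 63 per arm, 1:1 (total 126); power 80%; stated difference 0.6 SD (all from the sample size paragraph); two-sided alpha 0.05 (Statistical and Analytical Plan). The normal quantiles are 1.960 and 0.842.

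**1. Neighbouring figures, to confirm the plan's conventions.**
- Primary non-inferiority: 45% versus 55%, margin 15%, one-sided 0.025. n = (1.960 + 0.842)² × (0.55×0.45 + 0.45×0.55) / (0.10 + 0.15)² = 7.849 × 0.495 / 0.0625 = 62.2, so 63 per arm (power 80.5%). This reproduces.
- Proportions: 63 per arm, two-sided 0.05, 80% power. The detectable difference is 0.230, 0.244, 0.247 and 0.240 at base rates of 0.2, 0.3, 0.4 and 0.5. Around 0.25 reproduces.

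**2. The continuous figure.** For two means with difference d in SD units, the normal approximation is d = (z₀.₉₇₅ + z₀.₈₀) × √(2/n).
- d = (1.960 + 0.842) × √(2/63) = 2.802 × 0.1782 = 0.499 SD. The noncentral t gives 0.503 SD.
- Power at 0.6 SD: Φ(0.6/0.1782 − 1.960) = Φ(1.41) = 92.0%. The noncentral t gives 91.6%.
- Power at 0.5 SD: 80.1% (normal), 79.5% (t).
- n for 80% power at 0.6 SD: 2 × 7.849 / 0.36 = 43.6, so 44 per arm (normal) or 45 (t).

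The stated 0.6 SD at 80% power does not reproduce.

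**3. Could another test explain it?** A rank-sum test is approximated by multiplying n by its efficiency relative to the t-test.

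| Test | Effective n per arm | SD at 80% power | Power at 0.6 SD |
|---|---|---|---|
| t-test | 63 | 0.503 | 91.6% |
| Rank-sum, normal data (efficiency 0.955) | 60.2 | 0.515 | 90.4% |
| Rank-sum, worst case (efficiency 0.864) | 54.4 | 0.542 | 87.3% |

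None of these rounds to 0.6.

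**4. Which inputs would give about 0.6?** At 63 per arm unless noted, by the t calculation:
- Bonferroni over four tests: 0.603 SD.
- Two-sided 0.01: 0.617 SD.
- 90% power in place of 80%: 0.582 SD.
- 44 evaluable per arm at two-sided 0.05: 0.604 SD.

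The plan states none of these for this calculation.

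**5. The two missing-outcome statements.** Take a patient in remission at month 18 who is then lost.
- Sample size paragraph: non-responder.
- Analysis plan: the month-18 result is used, so responder.

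The two agree only when the month-18 result is also missing or is itself a failure.

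**The case against.** The strongest defence is attrition. QOL is also measured at month 12, and patients with less than a 25% fall in proteinuria leave the study at month 6, so their month-12 QOL is missing. The section on the MENTOR Remission Cohort expects 70% of randomized patients (88 of 126, or 44 per arm) to be in remission at the end of treatment, and 44 per arm gives 0.604 SD. If evaluable numbers did fall, 0.5 SD would be too optimistic for month 12: power there would be 75% at 57 per arm, 70% at 50 and 64% at 44 (assumed numbers).

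This does not rescue the sentence. The 70% is an expected remission rate, not a retention rate, and patients with at least a 25% reduction but no remission also stay. The sentence itself says 63 per arm, and month-6 data are collected from patients who exit. What stands is that 0.5 SD is right only for 63 evaluable per arm, and that the sponsor may have had an unstated allowance in mind.

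Three smaller objections are fair in part.
- The error is conservative: power at 0.6 SD is indeed at least 80%. That limits its weight but does not make the figure right.
- The planned QOL analysis is a mixed model, while the check uses two-group tests. The plan gives no within-patient correlation, so the planned model's power cannot be computed. A mixed model would not normally raise the detectable difference.
- The missing-outcome point is separate from the power figure. The analysis plan's rule is the more specific one, and being lost to follow-up need not mean the same as having no 24-month visit. The two texts still differ for the patient described above.

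**Conclusion.** The concern holds and is minor. With 63 evaluable patients per arm and two-sided 0.05, 80% power corresponds to about 0.5 SD (0.499 to 0.503). Power at 0.6 SD is about 92% (91.6% to 92.0%), some 12 points above the stated 80%. This rests on a two-group comparison of means with full data, and the rank-sum variants do not change it. The sample size, the design, the 0.25 for proportions and the primary power calculation are unaffected. The mismatch between the two missing-outcome statements is also real. It touches the scoring of the primary endpoint for some patients, but the power finding does not depend on it.

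**What to change.** In the sample size paragraph, do one of the following:
- replace 0.6 with about 0.5 standard deviations, and say that this assumes 63 evaluable per arm;
- keep 0.6 and state about 92% power;
- if 0.6 was meant to allow for missing QOL data or a stricter alpha, keep it and state the evaluable number or alpha used.

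Leave the total of 126 and the figure of around 0.25 as they are.

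Separately, state one rule for patients without a 24-month result in both the sample size paragraph and the primary endpoint analysis text.

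The cost is one figure in one sentence and one aligned clause. No change to sample size or design is needed, and the primary analysis model stays as it is.

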1.1 Overview

This prospective, randomized, controlled phase III nephrology study will determine whether rituximab is non-inferior to cyclosporine in inducing long-term remission of proteinuria in patients with idiopathic membranous nephropathy (IMN.) Subjects are randomized to open-label courses of treatment: IV rituximab (RTX), 1000 mg (2 infusions, 14 days apart), or oral cyclosporine (CSA) 3.5 to 5 mg/kg/day. Subjects are evaluated at 6 months; those that meet treatment response criteria will continue study medication and receive either 2 further infusions of RTX or a further 6 months of daily CSA treatment. Throughout the study period, laboratory and safety parameters will be collected and documented.

Study Hypothesis: B cell targeting with Rituximab is non-inferior to Cyclosporine in inducing long-term remission of proteinuria.

Comparison(s): IV rituximab (RTX), 1000 mg (2 infusions, 14 days apart; repeated at 6 months if a substantial reduction in proteinuria (equal to or >25%) is seen at 6 months) or oral cyclosporine (CSA) 3.5 to 5 mg/kg/day for 6 months (continued for another 6 months if a substantial reduction in proteinuria (equal to or >25%) is seen at 6 months).

SPECIFIC AIMS:

The specific aims of this Phase III trial are to test the hypothesis;

1. That B cell targeting with Rituximab is **non-inferior to** Cyclosporine in inducing **long-term remission** (complete or partial) of proteinuria in patients with IMN.
2. That B cell targeting with Rituximab **reduces the number of relapses (efficacy in sustaining remission) and increases the time to relapse when compared with treatment with Cyclosporine.**
3. That B cell targeting with Rituximab is **as effective as** Cyclosporine in inducing **complete or partial remission** of proteinuria in patients with IMN during the active treatment phase.
4. That B cell targeting with Rituximab has a better side effect profile and improved quality of life when compared with treatment with Cyclosporine in patients with IMN.

BACKGROUND AND SIGNIFICANCE

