5. ESRD
6. CR or PR, and CR alone at 6, 12, 18, and 24 months after randomization
7. Time to CR or PR
8. Effect of treatment on renal function, as assessed by slope of creatinine clearance from baseline to 24 months.

Table 1. Definition of remission status

Remission status	Proteinuria (UP g/24 hours) after treatment
Complete remission (CR)	UP \leq 0.3 g/24h and serum albumin \geq 3.5g/dl
Partial remission (PR)	Reduction in baseline UP of \geq 50% plus final UP \leq 3.5 g/24h but $>$ 0.3 g/24h
Non-response (NR)	Reduction in baseline UP of $<$ 25% (includes increase in UP)
Relapse	Development of nephrotic range proteinuria following CR or PR, i.e. $>$ 3.5g/24h

Patient recruitment

The study population will be comprised of individuals with biopsy-proven idiopathic MN. Total study size will be 126 patients, enrolled among up to 25 participating sites. Potential candidates for the study will be identified by the investigators using existing databases and clinical trial networks. The P.I. or the study coordinator will contact these potential candidates and if the preliminary interview indicates their willingness to participate, a consent form will be reviewed with the patient. If a potential candidate remains interested, the consent form will be signed, and the patient enrolled in the study. The institutional review board at each participating site will approve the recruitment process and consent forms. The Mayo Nephrology Collaborative Group (MNCG) will post information on its web site describing the study and identifying local contacts at the collaborating centers. Each site involved may have their own methods of informing and recruiting potentially eligible patients but in all cases will have IRB approval before embarking on this process. Each site will be expected to randomize approximately 6-10 patients over the recruitment period. If, based on site estimates of the IMN population that would be eligible for this study, we enroll approximately 30% of the annual population in a single year our recruitment will be complete. We have assembled a consortium for this trial with a population that well exceeds the enrollment needs based upon the multi-year enrollment plan for this trial.

Recruitment strategy

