The estimated duration of the study, given a 24-month enrollment period, a 2-year follow-up for each patient, and 1 year for data analysis is approximately 60 months. For those patients in the MENTOR remission cohort, their participation will be extended up to 3-years follow-up from the first day of study drug.

ANTICIPATED RESULTS

We believe RTX will be as effective as Cyclosporine in inducing complete and partial remissions in this patient population with membranous nephropathy.

PUBLICATION POLICY

A policy similar to the NIH policy on publication of study results will apply to this study. Details regarding policy statements may be found on the website at <http://www1.od.nih.gov/oma/manualchapters>. Any abstract or manuscript must be submitted to Genentech four weeks prior to submission as per contract.

REFERENCES

3. Cattran DC. Membranous nephropathy: quo vadis?[comment]. *Kidney international* 2002; **61**: 349-350.
10. Safai-Infanger M MB. Management of membranous nephropathy. *Nephrology Rounds - Stanford University* 2000; **3**: 1-5.

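### Aim 3 hypothesises that rituximab matches cyclosporine during treatment, but no planned analysis at months 6 and 12 can support it, so a non-significant test could be misread as equal efficacy

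*Combined protocol and SAP*

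**What the plan says.** - **Specific Aims, Aim 3.** This is listed among the hypotheses to be tested: RTX is "as effective as Cyclosporine in inducing complete or partial remission". The aim then sets the disease and the time frame: "of proteinuria in patients with IMN during the active treatment phase".
- **Patient monitoring and evaluation.** The phase is fixed in time: "The first 12 months of the study will be considered as the treatment period".
- **Secondary endpoints.** The matching endpoint is "CR or PR, and CR alone at 6, 12, 18, and 24 months after randomization". Aim 3 does not name visits. Months 6 and 12 follow from this endpoint together with the 12-month treatment period.
- **Statistical and Analytical Plan.** Two methods are named, a chi-square test and a logistic model with centre and baseline proteinuria as covariates. The text says that they "will also be used to compare the percent of patients with remission at 6, 12, 18, and 24 months". Ordinal and GEE comparisons are added. The same section says "Odds ratios and associated 95% confidence intervals will be estimated" and "Unless otherwise noted, all tests will be two-sided with alpha level 0.05". Nothing different is noted for months 6 or 12.
- **Sample size estimation.** The 15-point non-inferiority margin is defined on the proportions in remission at 24 months. No margin, power or decision rule is given for an earlier visit.
- **Anticipated Results.** The expected conclusion is repeated without a time point: "We believe RTX will be as effective as Cyclosporine in inducing complete and partial remissions".

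**The concern.** A test of no difference can contradict a similarity hypothesis, but failing to reject does not support it. Supporting it needs an interval judged against a stated margin, and none exists for the treatment phase. A significant result in favour of RTX would be a different claim, superiority.

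At stake is how the on-treatment comparison is reported. Without a criterion, a non-significant p-value at month 6 or 12 could be presented as confirming Aim 3. The fewer patients contribute, the more likely a non-significant p-value becomes when RTX is in truth worse.

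**Working it through.** **Inputs from Sample size estimation:** 63 per arm; month-24 design rates of 45% (CSA) and 55% (RTX); margin 15 points; one-sided alpha 0.025; remission on CSA in 60% to 75% of cases; RTX remission at 12 months of about 60%. **Input from the Statistical and Analytical Plan:** two-sided alpha 0.05. **Assumptions (not in the documents):** the true RTX deficits, and equal true rates in step 4.

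**1. The plan's own figure (month 24).** n = (1.960 + 0.842)² × (0.45×0.55 + 0.55×0.45) / (0.15 + 0.10)² = 7.849 × 0.495 / 0.0625 = 62.2, so 63 per arm. Power at 63 is Φ(0.25/0.0886 − 1.960) = 80.5%. The stated sample size is reproduced.

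**2. Difference test at an on-treatment visit.** Power = Φ[(d − 1.960 × s0) / s1], where d is the true deficit, s0 = √(2p̄(1−p̄)/63) with p̄ the mean of the two rates, and s1 = √((p1(1−p1) + p2(1−p2))/63).

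| CSA vs RTX | s0 | s1 | Power | Non-significant |
|---|---|---|---|---|
| 60% vs 45% | 0.0890 | 0.0880 | 39.1% | 60.9% |
| 70% vs 55% | 0.0863 | 0.0852 | 41.1% | 58.9% |
| 75% vs 60% | 0.0835 | 0.0824 | 43.5% | 56.5% |
| 60% vs 40% | 0.0891 | 0.0873 | 61.4% | 38.6% |

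Simulating the chi-square test for the three 15-point rows gives 58%, 57% and 56% non-significant, in line with the formula. A true 10-point deficit is non-significant in 77% to 80% of trials over the same CSA rates.

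**3. One possible result.** Take 38/63 on CSA against 28/63 on RTX, a deficit of 15.9 points. Pooled p̄ = 66/126 = 0.524 and z = 0.1587/0.0890 = 1.78, which is non-significant. The 95% interval for the deficit is 15.9 ± 1.960 × 8.79 points, or −1.3 to 33.1 points. This cannot be called similar efficacy, yet the planned test does not reject.

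**4. What a margin-based claim would need.** Suppose the month-24 margin of 15 points were carried over and the true rates were equal. Power = Φ(0.15/SE − 1.960) with SE = √(2p(1−p)/63), and n for 80% power = 7.849 × 2p(1−p)/0.0225.

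| Common rate | SE | 95% half-width | Power at 63 | n per arm for 80% |
|---|---|---|---|---|
| 60% | 0.0873 | 17.1 points | 40.5% | 168 |
| 70% | 0.0816 | 16.0 points | 45.1% | 147 |
| 75% | 0.0772 | 15.1 points | 49.4% | 131 |

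**The case against.** The strongest reply has four parts.

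- **Misreading is not planned.** A reader might infer that the plan will take a non-significant result as equal efficacy. No section says so, and Anticipated Results states a belief, not an analysis rule. This stands: the defect is an absent criterion, and misreading is a risk.
- **Intervals are planned.** A reader might infer that only p-values will be produced. In fact, odds ratios with 95% intervals are planned, and a wide interval would show that a meaningful deficit is not excluded. This lowers the risk but does not close the gap, because the intervals are on the odds-ratio scale and no margin is given on any scale for these visits.
- **An early RTX deficit is not the protocol's expectation.** A reader might infer that RTX is expected to act more slowly than CSA. Preliminary Studies says that proteinuria falls gradually after RTX, but likens this to prednisone with a cytotoxic agent and draws no comparison with CSA. Sample size estimation describes the 12-month RTX rate as close to that of calcineurin inhibitors, about 60%. The deficits in the working are therefore scenarios, and the mismatch does not depend on them.
- **It is a secondary matter.** Aim 3 is not the primary hypothesis, which limits the weight of the point. It is still one of four numbered aims worded as hypotheses to be tested.

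**Conclusion.** The point holds: Aim 3 is a similarity hypothesis, its planned analysis is a set of difference tests with odds-ratio intervals, and no margin or decision rule covers months 6 and 12. The plan can contradict Aim 3 but cannot support it. This follows from the text alone.

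The size is illustrative. With all 63 per arm counted, and ignoring covariate adjustment, a true 15-point RTX deficit would go undetected in about 57% to 61% of trials at CSA rates of 75% to 60%. A 20-point deficit (60% versus 40%) would go undetected in about 39%. The CSA rates are the plan's; the deficits are assumed.

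A reader might also infer that the 15-point margin can simply be reused. The documents do not support that: it was set for month 24 against an assumed 45% CSA rate, and nothing justifies it where CSA remission is put at 60% to 75%.

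**What to change.** In the Statistical and Analytical Plan, for Aim 3:

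1. Report the RTX minus CSA difference in the proportion with CR or PR at months 6 and 12 with its 95% confidence interval, alongside the odds ratios.
2. State that a non-significant test will not be taken as evidence of similar efficacy.
3. Reword Aim 3 as estimation of the on-treatment difference. This is the simpler course and needs no margin.

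Alternatively, keep the similarity wording, but allow the claim only if the lower 95% limit lies above a prespecified margin justified for the on-treatment period.

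Under either course, say how patients who leave at month 6 for lack of response, or who miss a visit, are counted at month 12. The stated missing-visit rule covers month 24 only.

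The cost is a few sentences, with no new patients, visits or data. The downside of the alternative is power of only about 40% to 49% with a 15-point margin and equal true rates of 60% to 75%, so the claim may often not be made even when it is true. That should be stated before the data are seen.
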